HUMAN OR ANIMAL MATERIAL TRANSPORTED FOR RESEARCH, DIAGNOSIS, DISEASE TREATMENT, ETC.

PATIENT SPECIMENS FOR WHICH THERE IS MINIMAL LIKELIHOOD THAT PATHOGENS ARE PRESENT AND ARE TRANSPORTED IN A PACKAGING WHICH

CONFIDENTIAL

WILL PREVENT ANY LEAKAGE ARE CONSIDERED “EXEMPT HUMAN SPECIMEN” OR “EXEMPT ANIMAL SPECIMEN”.

THEY MUST BE LABELED AS “EXEMPT HUMAN/ANIMAL SPECIMEN”.
THEY MUST USE TRIPLE PACKAGING SYSTEM.

Processing of samples in Urobiologics laboratory:

Urine samples are processed to remove non-hormonal redox compounds and then reacted with a redox indicator to evaluate each sample in the pair of urines as an oxidative or a reductive reaction.

Results are reported to the UM C.L.A.S.S. Laboratory according to the randomized numbers provided with the samples.

At the conclusion of the study the residual de-identified urine will be shipped to the Sponsor. Upon completion of processing, the sponsor will destroy all remaining materials and verify the destruction and disposition to the class laboratory.

Statistical power analysis and planned stat analysis:

From each experimental subject, we will have three non-overlapping pairs of consecutive urine samples taken. For each sample pair a blinded determination will be made by Urobiologics as to which sample in the pair was reductive. For the sake of simplicity, consider the case where these samples are collected in 6 consecutive months. Let “A” be the event that the reductive sample in the pair corresponds to the earlier cycle and “B” its converse. Then, the hypothesis of alternating reductive cycles is supported if the sequences AAA or BBB are over-represented relative to others. To analyze this, we will map whether the 2nd and 3rd pairs are successfully determined conditional

CONFIDENTIAL

on the first. Let “Y” denote success and “N” denote failure. Each subject then has one of the four patterns: YY, YN, NY, NN representing whether the 2nd and 3rd paired cycles are correctly predicted by the alternating cycle hypothesis. The hypothesis is supported by over-representation of YY relative to chance if predictions were made under the null of $P(Y) = 0.5$ with successive pairs called independently.

Consequently, we will first use a chi-squared goodness of fit test to evaluate the hypothesis below at the $\alpha=0.01$ level:

$H_0: p = 0.5$

and $P(YY) = p*p$; $P(YN) = P(NY) = p*(1-p)$; $P(NN) = (1-p)*(1-p)$.

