Under the alternative that $p = 0.75$, 37 subjects are needed to give 90% power to reject the null hypothesis at a significance level of 0.01. Assuming that <10% of enrolled subjects will be lost to attrition, we need to enroll a minimum of 40 subjects to achieve the target sample size.

Subsequently, we will estimate “p” in the model above using the total proportion of “Y” and form a confidence interval for this estimate using a bootstrap procedure to account for the pairing of samples within women. As a secondary analysis, we will use a likelihood ratio test to evaluate the validity of the independence assumption by comparing the one-parameter independence model to the four-parameter model with unique cell probabilities. Finally, for exploratory analyses to generate future hypotheses we will fit a mixed logistic regression in which the log odds of outcome “Y” are expressed as a linear function of any covariates to be explored and a random intercept inducing correlation between repeated measures within each woman.

Study Flow Chart

Study Procedure	Screening	Cycle 1	Cycle 2	Cycle 3	Cycle 4	Cycle 5	Cycle 6	All samples processed
Informed Consent	X							
Inclusion/Exclusion form	X							
Medical History/ Demographics	X							
Assign a Subject Number	X							

Give three urine collection kits to subject.
 
Each kit will contain two units. The two units provide for two collections about a month apart for each kit. Each unit will have one cup, one green-cap vial, one dropper, one instruction sheet, and one form to fill out with period start date and dates of collection of sample along with other relevant queries and instructions for returning the samples.
 
When the subject believes THAT she will likely ship her specimens back and not return samples in person, THE STUDY WILL PROVIDE THE APPROPRIATE MATERIALS TO SHIP THE SPECIMEN THAT COMPLY WITH ALL D.O.T. REGULATIONS. THE STUDY WILL PROVIDE THE TRIPLE PACKAGING (1- VIAL, 2 SEALED BAG, 3- ENVELOPE) RETURN ENVELOPES WITH PREPAID RETURN SHIPPING LABEL. THESE URINE SAMPLES ARE CONSIDERED INFECTIOUS SUBSTANCES CATEGORY B (SEE NOTE BELOW), THEREFORE TO COMPLY WITH D.O.T. REGULATIONS THE SAMPLE MUST CONTAIN THE TEXT: "EXEMPT HUMAN SPECIMEN" WHICH MUST BE VISIBLE ON OUTSIDE OF ENVELOPE. THIS EXEMPT STATUS IS FOR SPECIMEN SHIPPING ONLY AND DOES NOT IMPLY ANY IRB EXEMPTION.
	X*							
Determine if subject accepts reminders	X							

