Remind subjects at least twice in each cycle (when and as agreed by subject)		X	X	X	X	X	x	

CONFIDENTIAL

Receive urine samples, process in CLASS Lab per protocol.			X		X		X	
Send urine samples to Urobiologics			IN BATCHES OF SAMPLES					
Code data from Urobiologics			AS SAMPLES ARE REPORTED					
Quality assurance per protocol			AS SAMPLES ARE AVAILABLE					
Break blind; statistical analysis								X

*At any time, provide more kits if needed.

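### With six consecutive cycles, the primary test cannot tell alternation from a common tendency to call the earlier, older sample reductive, and no pre-specified analysis separates the two

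*Combined protocol and SAP*

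**What the plan says.** All statistical text is in the section on power and planned analysis. Each woman gives three non-overlapping pairs of samples. A pair is called A if the earlier sample is the reductive one and B otherwise. The plan works through one timing only: "For the sake of simplicity, consider the case where these samples are collected in 6 consecutive months". For that case, "the hypothesis of alternating reductive cycles is supported if the sequences AAA or BBB are over-represented relative to others".

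Pairs 2 and 3 are then scored Y or N given pair 1, "representing whether the 2nd and 3rd paired cycles are correctly predicted by the alternating cycle hypothesis", and "The hypothesis is supported by over-representation of YY relative to chance". The primary test is a chi-squared goodness of fit at the 0.01 level, with p = 0.5 under the null. Next come an estimate of p with a bootstrap interval, a likelihood ratio test of independence on the same four cells, and an exploratory mixed logistic model of Y, "expressed as a linear function of any covariates to be explored". No covariate is named.

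On timing, the Study Flow Chart says of a kit's contents: "The two units provide for two collections about a month apart for each" kit. The row "Receive urine samples, process in CLASS Lab per protocol" is marked at cycles 2, 4 and 6. Step 1 of the sample preparation expects the two vials to be about 25 to 35 days apart, and step 9 stores them at room temperature. Tubes go to the sponsor under random numbers. The QA section allows other pairings, such as months 2 and 3, but as an option, with no number of pairs, test or threshold.

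**The concern.** A and B are defined by time order, and time order within a pair is also sample age. Scoring pairs 2 and 3 only for agreement with pair 1 discards the direction. A run of AAA in most women would be expected if the older sample simply tended to read as reductive. A mixture of AAA and BBB would be expected if women alternate and enter the study in either phase. The primary test gives both patterns the same score. Random tube numbers hide the order from the assay laboratory, but they do not remove a physical difference in age.

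The stated objective is to determine whether alternation exists. If a sizeable order effect were present, a significant primary result could be reported as alternation when order alone explains it. The raw A/B calls that would show this are collected, but no analysis or report of them is planned.

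**Working it through.** **Inputs.** From the plan: four cells, null p = 0.5, alpha 0.01, alternative p = 0.75, 37 evaluable and 40 enrolled. Assumed: a, the probability that the earlier sample is called reductive when there is no alternation. The documents give no value for it.

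**The plan's own figure.** Under p = 0.75 the cells are 0.5625, 0.1875, 0.1875 and 0.0625, against 0.25 each. Then w² = [(0.3125)² + 2(0.0625)² + (0.1875)²]/0.25 = 0.5625. The noncentral chi-squared with 3 df gives 35 women for 90% power. Exact multinomial enumeration at n = 37 (critical value 11.345) gives 91.0% power and a true size of 0.87%. The stated 37 is sound, and the test holds its level for the null as written.

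**Order only, consecutive cycles.** Each pair is called A with probability a, independently:
- P(YY) = P(AAA) + P(BBB) = a³ + (1−a)³
- P(YN) = P(AAB) + P(BBA) = a²(1−a) + (1−a)²a = a(1−a)
- P(NY) and P(NN) are also a(1−a)

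**Alternation, call accuracy a.** A woman whose earlier cycle is truly reductive is called A with probability a in every pair. A woman in the opposite phase is called B with probability a. In either phase P(YY) = a³ + (1−a)³ and the other cells are a(1−a). The four probabilities are identical, so every statistic built on these cells behaves the same way under both explanations. That includes the chi-squared test, the estimate of p and the likelihood ratio test.

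**Rejection by the planned test with no alternation (exact, n = 37):**

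| a | P(YY) | other cells, each | rejects |
|---|---|---|---|
| 0.50 | 0.25 | 0.25 | 0.87% |
| 0.60 | 0.28 | 0.24 | 1.2% |
| 0.65 | 0.3175 | 0.2275 | 3.0% |
| 0.70 | 0.37 | 0.21 | 10.5% |
| 0.75 | 0.4375 | 0.1875 | 33% |
| 0.80 | 0.52 | 0.16 | 71% |

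From a = 0.70 upward, almost all rejections have YY as the largest cell (for example 10.3 of the 10.5 points at 0.70). With all 40 women the last three rows become 12%, 37% and 76%.

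**Skipped cycles.** If one cycle is missed between pairs 1 and 2, alternation predicts the reverse order afterwards. For such a woman, order alone gives P(NN) = a³ + (1−a)³ and P(YY) = a(1−a). Suppose 8 of 37 women do this (an assumption) and are coded as alternation predicts. Exact rejection with YY largest then falls to about 14% at a = 0.75 and 37% at 0.80.

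**What the discarded direction shows.** At a = 0.75, order alone gives 37 × 0.4219 = 15.6 AAA and 37 × 0.0156 = 0.6 BBB. Alternation with equal starting phases gives 37 × 0.21875 = 8.1 of each.

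**A test that keeps direction.** Take the number of YY women, and shuffle the raw A/B calls across women within each pair position (one-sided 0.01, n = 37, simulated).
- Common order effect, no alternation: rejects in about 0.4% to 0.7% for a from 0.5 to 0.9.
- Alternation at accuracy 0.854, where P(Y) = 0.75: power is about 99% with starting phases 50:50, 82% at 80:20, 46% at 90:10, and about 0 if all women start alike.
- Order effects that differ between women (about half at 0.5, half at 0.8 or 0.9), no alternation: rejects in about 7% and 26%, against 14% and 58% for the primary test.

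**The case against.** The harm depends on a quantity that nobody has measured. The documents report no order or age effect. They also state that "Urine samples are processed to remove non-hormonal redox compounds and then reacted with a redox indicator", which may keep a near 0.5. Home collection and handling are in Appendix 1, which was not available for this review. Tubes are shipped in batches, so both members of a pair may be much older than the month between them. All of this stands, and it limits the weight of the point.

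The consecutive case is a declared simplification, discarded collections are expected, and odd gaps weaken the confounding. This also stands, but the plan does not show how Y is coded after a skipped cycle.

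The QA re-pairing of months 2 and 3 could expose a strong order effect, and the exploratory model could include the direction of pair 1. Both are real but partial. QA is optional and has no analysis or threshold, and the model names no covariate.

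A reader might infer that the primary test is invalid, that its type I error is inflated, or that an age effect is present. The documents support none of these. The size is 0.87% under the stated null, and the table describes a hypothetical departure from it. A reader might also infer that agreement of a direction-keeping test would exclude order altogether. It would not, as the figures for effects that differ between women show.

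**Conclusion.** The point holds as one of interpretation. With consecutive cycles, a significant primary result does not by itself distinguish alternation from a common order or sample-age effect, and no pre-specified analysis does so. The algebra is exact and needs no assumption about starting phases. The practical size rests wholly on a. It is negligible near 0.5, small below about 0.65, and serious from about 0.70 upward, and missed cycles reduce it. This should be fixed because the remedy is cheap and uses data already collected. It gives no reason to replace the primary test or change the sample size. Confidence is medium, because no order effect is documented.

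**What to change.** Keep the primary test and the sample size. Add three items to the SAP before the blind is broken:

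1. Report the AAA and BBB counts and the overall proportion of A calls, with an interval clustered by woman. Keep this descriptive, because unbalanced starting phases also move the proportion.
2. Pre-specify a supporting permutation test of the number of YY women (one-sided 0.01), shuffling raw A/B calls across women within each pair position. Hold each woman's gap pattern fixed, and code Y as the direction that alternation predicts after any skipped cycles, with one worked example.
3. State how the results will be read. A significant primary result alone does not exclude an order effect. Agreement of the supporting test argues against an order effect common to all women, but not against order effects that differ between women. A non-significant supporting test does not disprove alternation and does not gate the primary conclusion.

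The cost is wording and a short program, with no new samples or visits. The SAP should state the main downside: the supporting test loses power as starting phases become unbalanced and has almost none if all women start alike. Any QA re-pairing can stay at the statistician's discretion.

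### The primary four-cell chi-square has no direction, yet only an excess of YY supports the hypothesis; a one-sided exact test on the YY count would match the stated criterion

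*Combined protocol and SAP*

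**What the plan says.** All of this is in the combined protocol and SAP, under the heading Statistical power analysis and planned stat analysis.

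- Criterion in sequence terms: "the hypothesis of alternating reductive cycles is supported if the sequences AAA or BBB are over-represented relative to others".
- The second and third pairs are then scored against the first: "Each subject then has one of the four patterns: YY, YN, NY, NN". YY is the same event as AAA or BBB, and the criterion is restated as "The hypothesis is supported by over-representation of YY relative to chance".
- Primary test: "we will first use a chi-squared goodness of fit test to evaluate the hypothesis below at the" 0.01 level. The null is p = 0.5 with the two calls independent, so every cell has probability 0.25.
- Power: "Under the alternative that $p = 0.75$, 37 subjects are needed to give 90% power", where power means the probability "to reject the null hypothesis at a significance level of 0.01". No direction is attached.
- Afterwards, p is estimated from the overall proportion of Y with a bootstrap interval. No confidence level is given, and the interval has no stated part in the decision.

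**The concern.** The plan states a directional criterion and then adopts a test without direction. The Pearson statistic squares each cell's deviation, so exchanging the YY and NN counts leaves it unchanged. A significant result may reflect too many YY, too many NN, or an imbalance between YN and NY, and only the first supports alternation.

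This is a validation study of one directional claim, and the analysis is run after the blind is broken. If the test rejects without a YY excess, or YY is clearly in excess and the test does not reject, the plan does not say what is concluded. A rule settled after seeing such a table is open to choice. The test also spends rejection probability on patterns that nobody hypothesises, which costs power when the effect is smaller than planned.

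**Working it through.** **Inputs.** From the statistical section: four cells; null 0.25 per cell; alpha 0.01; alternative p = 0.75; 37 evaluable and 40 enrolled women. The degrees of freedom are not stated. A fully specified four-cell null with no estimated parameter gives 3, with critical value 11.345.

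**Reproducing the plan's figure.** At p = 0.75 the cells are 0.5625, 0.1875, 0.1875 and 0.0625. The effect size is

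w² = [(0.3125)² + 2(0.0625)² + (0.1875)²] / 0.25 = 0.5625.

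At n = 37 the noncentrality is 37 × 0.5625 = 20.81, and the noncentral chi-square on 3 df gives 92.7% power. Enumerating every four-cell table gives an exact power of 91.0% at n = 37, first passing 90% at n = 36 (90.3%). The stated 37 is therefore right, and it fits the 3-df test (the same noncentral formula gives 35 on 3 df, but 27 on 1 df and 31 on 2 df).

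**Direction of rejection (exact, n = 37).**
- Power is 91.0% at p = 0.75 and 91.0% at p = 0.25.
- Null size is 0.0087, of which 0.0033 has YY above its expected 9.25. So 0.0054 / 0.0087, about 62.5% of false rejections, do not meet the plan's criterion. At n = 40 the figures are 0.0098 and 0.0036.

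**Example tables (YY/YN/NY/NN, n = 37, expected 9.25 each).**
- 9/18/5/5: (0.0625 + 76.5625 + 18.0625 + 18.0625) / 9.25 = 12.19, p = 0.0068. The test rejects with YY below expectation. The proportion of Y is (2 × 9 + 18 + 5) / 74 = 41/74 = 0.55, so the estimate of p points upward all the same.
- 18/7/6/6: (76.5625 + 5.0625 + 10.5625 + 10.5625) / 9.25 = 11.11, p = 0.011. The test does not reject, although the one-sided exact p for YY, P(Bin(37, 0.25) ≥ 18), is 0.0016.
- 21/7/7/2 and 2/7/7/21 both give 21.70, p = 0.00008. Their one-sided exact p-values for YY excess are 0.00004 and 0.9997.

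**Power of directional alternatives.** The YY test uses Bin(n, 0.25) and the total-Y test uses Bin(2n, 0.5), each one-sided at 0.01. Cut-offs and sizes are:
- n = 37: YY ≥ 17 (size 0.0045); total Y ≥ 48 of 74 (size 0.0070).
- n = 40: YY ≥ 18 (size 0.0047); total Y ≥ 51 of 80 (size 0.0092).

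Two models are shown. The first is the plan's independence model. The second is an assumption of this review: each pair is read correctly with probability q, and Y2 and Y3 share any error in the first pair. Then YY = q³ + (1−q)³ and each other cell is q(1−q), with q = [1 + √(2P(Y) − 1)] / 2.

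| Model | P(Y) | n | Planned chi-square | YY count | Total Y |
|---|---|---|---|---|---|
| Independence | 0.75 | 37 | 91.0% | 92.3% | 98.1% |
| Independence | 0.75 | 40 | 94.4% | 94.4% | 99.1% |
| Independence | 0.70 | 37 | 65.7% | 70.3% | 86.2% |
| Independence | 0.70 | 40 | 72.6% | 74.6% | 90.8% |
| Shared error | 0.75 | 37 | 96.6% | 98.7% | 96.4% |
| Shared error | 0.75 | 40 | 97.9% | 99.2% | 98.0% |
| Shared error | 0.70 | 37 | 81.7% | 89.8% | 83.2% |
| Shared error | 0.70 | 40 | 85.9% | 92.3% | 88.0% |

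Part of the gain comes from placing the whole 0.01 on one side. Total Y at one-sided 0.005 (49 or more of 74) has 96.7% at p = 0.75 and 80.0% at p = 0.70. The YY cut-off of 17 at n = 37 already meets one-sided 0.005, since its size is 0.0045.

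**Keeping the chi-square with a YY-excess condition** costs 0.001 percentage points of power at p = 0.75 and 0.01 at p = 0.70 (n = 37, independence).

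**The case against.** The strongest reply is that direction is already in the plan. The criterion is stated twice before the test is named, nothing claims that rejection alone proves alternation, and the estimate of p with its interval will show which way the data lean. On that reading 9/18/5/5 is simply not support, 18/7/6/6 is an ordinary near-miss, and one clarifying sentence would do. Under the planned effect a rejection without YY excess is almost impossible (probability 0.0000086 at n = 37), and the YY test gains only 1.3 points there and nothing at n = 40. If the plan's independence model is trusted, total Y is the stronger directional test.

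Much of this stands. The intended direction is clear, and a careful reader would not call an NN excess support. The near-miss table shows a loss of sensitivity to the stated criterion, not a logical contradiction. The gain at p = 0.75 is small, and the preference for YY over total Y on power rests on the shared-error assumption.

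What does not stand is that the follow-on estimate closes the gap. It is not tied to the decision, and it does not isolate YY. With YY = NN = 0.4375, p is exactly 0.5, yet the chi-square rejects 97.5% of the time. In 9/18/5/5 the estimate leans upward while YY is not in excess. Nor is the replacement test mere preference: at p = 0.70 under independence it has more power at every evaluable number from 36 to 40 (for example 76.2% against 64.6% at 36, and 79.8% against 70.5% at 39).

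**Conclusion.** The concern holds. The primary test does not match the plan's criterion, and rejection alone does not show the pattern that the plan calls support. At 37 women about three-eighths of the test's null rejection probability (0.0033 of 0.0087) lies on YY excess. The power lost relative to a YY test under independence is 1.3 points at p = 0.75 and 4.6 points at p = 0.70.

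This is not a sample-size error, since 37 women do give 90% power. Nor is it inflated type I error, since the error rate in the claimed direction is below 0.01. It is a change that should be made, not one on which the trial's validity turns.

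The result rests on 3 df, which is inferred but agrees with the stated sample size, and on the plan's independence model except where the shared-error assumption is named. One limit remains under any of these tests: a consistent earlier-versus-later difference within pairs would also produce AAA or BBB, so a directional test matches the criterion without excluding that explanation.

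**What to change.** Before the blind is broken, name one directional primary test. The recommended choice is a one-sided exact binomial test at 0.01 that the proportion of women with YY exceeds 0.25. Write it as a rule for whatever number is evaluable; the cut-offs are 16 at 36 women, 17 at 37, 38 or 39, and 18 at 40. This tests the stated criterion, and it is the better directional test if Y2 and Y3 share the first pair's error. If the sponsor prefers to rely on the independence model, a one-sided exact test of total Y against 0.5 is the alternative. Choose one, not both. Keep the four-cell chi-square as a descriptive check of fit.

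At minimum, keep the planned test and add one sentence: rejection counts as support only when the YY count exceeds its expected count.

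The cost is wording in the statistical section, with no added women or samples. The downside is that patterns other than YY excess could no longer carry a formal primary claim, and the trial does not hypothesise any.

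### The secondary likelihood ratio test of independence also tests whether pairs 2 and 3 have equal success rates, so a rejection cannot be attributed to dependence

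*Combined protocol and SAP*

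**What the plan says.** All of this is in the section *Statistical power analysis and planned stat analysis*. Pairs 2 and 3 are each scored Y or N against the first pair: "Each subject then has one of the four patterns: YY, YN, NY, NN representing whether the 2nd and 3rd paired cycles are correctly predicted" under the alternating-cycle hypothesis. The null has p = 0.5 "with successive pairs called independently". The model is written with one p: P(YY) = p², P(YN) = P(NY) = p(1−p), P(NN) = (1−p)².

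Three analyses follow from it. For the primary one, "we will first use a chi-squared goodness of fit test to evaluate the hypothesis below", at α = 0.01. Next, p is estimated "in the model above using the total proportion of" Y, with a bootstrap interval that allows for the pairing within women. The secondary analysis is a "likelihood ratio test to evaluate the validity of the independence assumption by comparing the one-parameter independence model to the four-parameter model", the latter having a free probability for each cell. No significance level, degrees of freedom or decision rule is given for it, and no separate test of equal rates in pairs 2 and 3 is planned.

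**The concern.** The one-parameter model contains two restrictions:

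- Y2 and Y3 are independent within a woman.
- P(Y2) = P(Y3), which under independence is the same as P(YN) = P(NY).

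The saturated model relaxes both, but the plan describes the comparison as a check of the first only. If pair 3 conforms less often (or more often) than pair 2, the test can reject although the calls are independent, and the result would be reported as dependence. The rate difference, which affects how the single pooled p should be read, would go unnamed. In the opposite case, with equal rates and real dependence, one of the two degrees of freedom is spent on a restriction that holds, and power falls.

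**Working it through.** **The plan's own figure.** The documents give a number for the primary test only: "Under the alternative that $p = 0.75$, 37 subjects are needed" for "90% power to reject the null hypothesis at a significance level of 0.01". Under p = 0.75 the cells are 9/16, 3/16, 3/16, 1/16, against 1/4 each.

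w² = Σ(p1 − p0)²/p0 = 4 × (0.3125² + 2 × 0.0625² + 0.1875²) = 0.5625.

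With 3 df and α = 0.01, the noncentral chi-square reaches 90% power at n = 35 and gives 92.7% at n = 37. Exact enumeration at n = 37 gives 91.0% power and size 0.0087. The stated 37 is therefore reproduced and is not in question.

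**Degrees of freedom of the secondary test.** Four cell probabilities that sum to 1 leave 3 free parameters. The null has 1, so the reference is 3 − 1 = 2 df. The statistic splits exactly:

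G²(one p vs saturated) = G²(separate p2, p3 under independence vs saturated; 1 df) + G²(one p vs separate p2, p3; 1 df).

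Only the first component concerns independence. This is algebra and needs no assumed rates.

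**Method for the figures below.** All tables (YY, YN, NY, NN) with n = 37 were enumerated and weighted by their multinomial probabilities. The level (5%, with 1% alongside), the unequal rates and the correlations are assumptions, because the documents give none for this test.

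**Independent calls: how often independence is rejected**

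| P(Y2) / P(Y3) | Planned 2 df, 5% | 1-df LR, 5% | Fisher, 5% | Planned, 1% | 1-df LR, 1% |
|---|---|---|---|---|---|
| 0.75 / 0.75 | 6.1% | 6.7% | 2.6% | 1.3% | 1.3% |
| 0.80 / 0.70 | 14.4% | 6.9% | 2.5% | 4.8% | 1.3% |
| 0.85 / 0.65 | 43.1% | 7.3% | 2.1% | 22.5% | 1.3% |
| 0.90 / 0.60 | 80.6% | 7.1% | 1.6% | 61.2% | 1.0% |

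Hand check of the 0.85/0.65 row. The true cells are 0.5525, 0.2975, 0.0975, 0.0525. The closest one-p model has p = 0.75, with cells 0.5625, 0.1875, 0.1875, 0.0625. The noncentrality is 2 × 37 × Σ p·ln(p/p0) = 74 × 0.0545 = 4.03, for which a 2-df test at 5% has asymptotic rejection probability 41.9%, close to the exact 43.1%.

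**Dependent calls, both rates 0.75: power at 5%**

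| Correlation | Planned 2 df | 1-df LR | Fisher |
|---|---|---|---|
| 0.3 | 31.2% | 41.9% | 37.9% |
| 0.4 | 51.4% | 63.7% | 60.0% |

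The gaps to the 1-df likelihood ratio test are 41.9 − 31.2 = 10.7 and 63.7 − 51.4 = 12.3 points. That test has slightly higher size (6.7% against 6.1%), so a small part of the gap is size. With both tests held to about 5% size at p = 0.75, the figures are 27% against 37% and 47% against 59%.

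A correlation in this range can arise from the scoring itself. Suppose every woman alternates and each pair is called correctly, independently, with probability c. Then P(Y) = c² + (1−c)² and P(YY) = c³ + (1−c)³. Setting P(Y) = 0.75 gives c ≈ 0.854, P(YY) = 0.625 and correlation (0.625 − 0.5625)/0.1875 = 1/3. Power there is 38% for the planned test and 49% for the 1-df test. This error model is an assumption, not something the plan states.

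**Unequal rates with dependence: power at 5%**

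| P(Y2) / P(Y3), correlation | Planned 2 df | 1-df LR |
|---|---|---|
| 0.80 / 0.68, 0.51 | 86.2% | 86.3% |
| 0.85 / 0.65, 0.3 | 71.4% | 45.0% |

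In the last row the extra rejections of the planned test come from the rate difference, not from better detection of dependence.

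**The case against.** The strongest defence is that this is a sound overall check of the model the plan uses. A rejection does say that the one-parameter model does not fit, and the four cell counts would show where. That stands for a test of overall fit. The plan, however, names independence as the target, and a 2-df rejection does not establish that.

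Second, nothing decisive depends on the test. It is secondary and has no level or decision rule. The bootstrap, read as resampling whole women, remains valid for the average rate under dependence and under unequal rates. This stands in full.

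Third, the large false-rejection rates need large gaps: 43% needs 20 points between the pairs and 81% needs 30. At 0.78/0.72 the planned test rejects 8.9%. Nothing in the documents says that the rates differ, and constant call accuracy would make them equal. The size of the problem is therefore conditional; that a rejection cannot be attributed is not.

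Fourth, the planned exploratory mixed logistic model could include pair order as a covariate. It does not name it, so the cover is partial.

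A reader might also infer that the planned test is always weaker against dependence. The unequal-rate results show that it is not.

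**Conclusion.** The point holds as one of interpretation for a secondary analysis. The planned test combines independence with equal rates in pairs 2 and 3, so a rejection cannot be reported as dependence. With 37 women and independent calls it rejects 14% at 0.80/0.70 and 43% at 0.85/0.65 at the 5% level (5% and 23% at 1%), and about 6% when both rates are 0.75. When the rates are equal it loses about 10 to 12 power points at correlations of 0.3 to 0.4, a small part of which is the 1-df test's higher size. When the rates differ there may be no loss. The structure of the test follows from the plan's own formulas, while the rates, correlations and 5% level are assumptions.

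A reader might infer that the trial's main result is at risk. The documents do not support that: the primary test, its α, the 37 evaluable and 40 enrolled women, the estimate of p and its bootstrap interval do not depend on this test.

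**What to change.** Replace the sentence on the secondary test with the following, all on the same 2×2 table of Y2 by Y3:

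1. **Independence.** Compare the independence model with separate p2 and p3 against the saturated model (1 df), with Fisher's exact test as the small-sample version. State the level and degrees of freedom. Draw conclusions about independence from this test only.
2. **Equal rates.** Report p2, p3 and their paired difference with a confidence interval, with the exact McNemar test of YN against NY. Present them beside the pooled p, described as the average rate over pairs 2 and 3.
3. **Reading of the McNemar result.** State that a non-significant result is not evidence of equal rates. With 37 women and independent calls at 0.80/0.70 the exact test rejects only 10.7% of the time at the 5% level, so the interval should carry the interpretation.

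The cost is one or two sentences and one extra secondary p-value. No new data or women are needed, and the primary analysis does not change.
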